8.9 Concomitant medication

A participant's concomitant medication should be checked by a medically qualified investigator before randomisation to ensure eligibility and to ensure appropriate action is taken regarding concomitant medication.

Participants prescribed or taking prohibited medicines as listed in Appendix 2 are ineligible for the study unless in the investigator's opinion the interacting medicine can safely and appropriately be withheld for the duration of clarithromycin treatment plus 3 days. Should an indication for these drugs develop during the study treatment period and treatment with a prohibited medicine commence, participants must be withdrawn from study clarithromycin treatment. Participants will also permanently stop trial clarithromycin treatment should clarithromycin (or other macrolide) become clinically indicated for antibiotic treatment as per local antimicrobial policies. Relevant data should continue to be collected on participants providing consent is still in place.

Participants prescribed or taking medication listed in Appendix 3 can be enrolled in the study at investigator discretion following consideration of advice contained in the protocol, the BNF and the SmPC.

8.10 Assessment of adherence with treatment

Administration of clarithromycin for all participants will be assessed from routine hospital medicine administration records. Sponsor does not require any additional records to be maintained over and above usual local practice for traceability purposes for those assigned to the intervention arm.

8.11 Name and description of each Non-Investigational Medicinal Product (NIMP)

The comparator for the CLASP study will be usual non-macrolide antibiotic care according to local hospital guidelines. Therefore, there will be no NIMPs in the study.

8.12 Usual care

Usual care will likely vary between sites but should not include macrolide antibiotics. All participants will receive antibiotics as part of usual care and this will often be a penicillin. If a participant in the usual care arm develops a clinical indication for macrolide antibiotics and these are needed for clinical reasons, they can continue in the study but this will be recorded.

9 PHARMACOVIGILANCE

9.1 Definitions

| | Term Definition |
|--|-----------------|
|--|-----------------|

| Adverse Event (AE) | Any untoward medical occurrence in a participant to whom a medicinal product has been administered, including occurrences which are not necessarily caused by or related to that product. |
|--|--|
| Adverse Reaction (AR) | An untoward and unintended response in a participant to an investigational medicinal product which is related to any dose administered to that participant. |
| | The phrase "response to an investigational medicinal product" means that a causal relationship between a trial medication and an AE is at least a reasonable possibility, i.e. the relationship cannot be ruled out. |
| | All cases judged by either the reporting medically qualified professional or the Sponsor as having a reasonable suspected causal relationship to the trial medication qualify as adverse reactions. It is important to note that this is entirely separate to the known side effects listed in the SmPC. It is specifically a temporal relationship between taking the drug, the half-life, and the time of the event or any valid alternative aetiology that would explain the event. |
| Serious Adverse Event (SAE) | A serious adverse event is any untoward medical occurrence that: |
| Note: SAEs are further defined in section 9.2 in line with risk adaptation for this trial | Results in death Is life-threatening Requires inpatient hospitalisation or prolongation of existing |
| | hospitalisation Results in persistent or significant disability/incapacity Consists of a congenital anomaly or birth defect |
| | Other 'important medical events' may also be considered serious if they jeopardise the participant or require an intervention to prevent one of the above consequences, e.g. emergency interventions within A&E departments that do not result in hospitalisation such as administration of glucagon/glucose in participants with hypoglycaemia. |
| | NB: The term "life-threatening" in the definition of "serious" refers to an event in which the participant was at risk of death at the time of the event; it does not refer to an event which hypothetically might have caused death if it were more severe. |
| Serious Adverse Reaction (SAR) | An adverse event that is both serious and, in the opinion of the reporting Investigator, believed with reasonable probability to be due to one of the trial treatments, based on the information provided. |
| Suspected Unexpected Serious Adverse Reaction (SUSAR) | A serious adverse reaction, the nature and severity of which is not consistent with the information about the medicinal product in question set out in the reference safety information. |

NB: To avoid confusion or misunderstanding of the difference between the terms "serious" and "severe," the following note of clarification is provided: "Severe" is often used to describe intensity of a specific event, which may be of relatively minor medical significance. "Seriousness" is the regulatory definition supplied above.

9.2 Operational definitions for (S)AEs

Clarithromycin has been in clinical use for more than 30 years and is widely used for the treatment of respiratory tract infections, including community acquired infection. The IMP is generally well tolerated with the most common side effects being mild gastrointestinal adverse reactions. It has a well-defined safety profile obtained throughout the lifetime of the drug and therefore it is highly unlikely that this trial will identify any novel (serious) adverse reactions. Participants are anticipated to exhibit complications related to the index stroke, associated complications, and comorbidities resulting in prolongation of hospitalisation and high numbers of adverse events due to the short time frame between the index stroke and the commencement of treatment with IMP. In addition, participants may receive multiple treatments to manage stroke symptoms, and associated underlying medical conditions. Under these circumstances, participants may be subject to multiple ongoing adverse events and serious adverse events and it may be difficult for investigators to distinguish AEs and SAEs that are a consequence of disease processes and concomitant medications from those that have a causative relationship with the IMP(s) due to a high level of confounders. Taking the above into account, (S)AEs (except for those detailed below) will not be reported via the eCRF but must be recorded within participant medical records in accordance with GCP.

The principal risk associated in adding clarithromycin to the usual care pathway is the potential for prolongation of the QT and QTc interval resulting in cardiac arrythmias; primarily ventricular arrythmias. In addition, treatment with antimicrobial therapies, including macrolides, can be associated with an increased risk of developing infection with *C.difficule*. While cardiac arrythmias and *C.diff* infections may not necessarily always meet the regulatory definition of serious, they will almost certainly require intervention to prevent them from become so and are significant medical events.

Therefore, the following events will be subject to expedited reporting as serious adverse events from the point of randomisation until day 3 post cessation of trial IMP (generally, day 7 or earlier but could be up to day 10 after randomisation):

- Any suspected or confirmed infection with *C.difficile* irrespective of whether the event meets the regulatory definition of serious.
- Any incidence of sustained (>30s) ventricular arrythmias irrespective of whether the event meets the regulatory definition of serious.
- Any serious adverse event suspected to be directly related to the IMP that is considered unexpected by the local investigator.

Note: If an event occurs more than 72 hours after cessation of IMP that is considered related to IMP, it must be reported.

Hospitalisation, or prolongation of hospitalisation, related to the index stroke and associated complications, or other underlying medical conditions are excluded from reporting as a serious adverse event for the purpose of this trial. Such events should be recorded within the eCRF at visit 2 and visit 3 (day 90) as per routine data collection and will be used to inform trial endpoints. The IDMC will review event rates on a regular basis to ensure the frequency of these events is line with expectations.

The following are exempted from recording within the eCRF and reporting as SAEs:

- Routine treatment or monitoring of the studied indication not associated with any deterioration in condition.
- Treatment that is elective or pre-planned, for a pre-existing condition not associated with any deterioration in condition, e.g. pre-planned hip replacement operation which does not lead to further complications.
- Any admission to hospital or other institution for general care where there was no deterioration in condition.
- Treatment on an emergency, outpatient basis for an event not fulfilling any of the definitions of serious as given above and not resulting in hospital admission.

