3.3.2 Secondary outcomes

- All-cause mortality at 90 days
- Days spent in pre-admission usual place of residence at 90 days
- Cardiovascular mortality at 90 days
- Non-elective admissions by 90 days
- Stroke at 90 days
- Major cardiovascular events at 90 days
- EQ-5D-5L at 90 days
- Stroke Impact Scale at 90 days
- Zarit Caregiver Burden (ZBI-12) interview
- Clostridioides difficile infection within 90 days
- Ventricular arrhythmia within 7 days
- Health and social care resource use (index hospitalisation and post-discharge health and social care contact) up to 90 days to inform health economic analysis.

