6.2 Exclusion criteria

- Requirement for macrolide therapy as usual care
- Confirmed respiratory viral infection (e.g. COVID-19, influenza) at point of screening*
- Known antibiotic treatment for chest infection or pneumonia within the last two weeks (single doses or less than 3 days of treatment is allowed)
- Known toxin positive *C.difficile* infection in the past 12 weeks
- Contraindications or major cautions to macrolide antibiotic use:
 - Known hypersensitivity to clarithromycin, its excipients or other macrolide antibiotics
 - Established diagnosis of myasthenia gravis
 - Diagnosis of long QT syndrome
 - QTc interval >460ms on last ECG before screening[†][36]
 - Known hypokalaemia (K+ < 3.5 mmol/l) which has not been corrected

- Known hypomagnesaemia (Mg2+ < 0.70 mmol/l) which has not been corrected
- History of ventricular tachycardia
- History of cardiac arrest
- Severe hepatic impairment defined as AST, ALT or bilirubin > 3 times ULN or known diagnosis of cirrhosis
- Current use of medicine(s) known to increase risk of QT prolongation that in the opinion of the investigator cannot reasonably be withheld for the duration of study treatment plus 3 days (see Appendix 2)
- Current use of medicine(s) that are contra-indicated in combination with clarithromycin that in the opinion of the investigator cannot reasonably be withheld for the duration of study treatment plus 3 days (see Appendix 2)
- Women of childbearing potential who are pregnant, breastfeeding or who are unwilling to use appropriate contraception or abstain from sexual intercourse for 3 days (72 hours) after the last dose of clarithromycin (see Appendix 1 for definitions and information on acceptable methods of contraception)
- Plan for imminent mechanical ventilation
- End-of-life care
- Previously randomised into the CLASP study

* A test for viral infection is not required by protocol, this is only if it is done for routine clinical care.

[†]Some ECG machines may provide different measures of QTc. For trial eligibility, the longer result should be used.

Co-enrolment in other Clinical Trial of Investigational Medicinal Products (CTIMPs) is not permitted while participating in CLASP. Co-enrolment in observational studies, diagnostic studies or other research may be permitted subject to agreement of the Sponsors and Chief Investigators of both studies.

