7.9 Withdrawal criteria

7.9.1 Withdrawal from clarithromycin treatment (intervention arm)

Participants may be withdrawn from the study treatment by local clinical teams in the event of a Serious Adverse Reaction (SAR) and it is felt that it is in the best interest of the patient to discontinue treatment. Participants allocated to the intervention arm will also be withdrawn from clarithromycin treatment in the event:

- Treatment is initiated with a prohibited medicine, where the prohibited medicine has not been temporarily discontinued by the local PI (see Appendix 2)
- Requirement for macrolide therapy as part of evolving antibiotic use
- Known toxin positive *C.difficile* infection
- The participant deteriorates after enrolment and becomes for palliative care only
- Onset of contraindications or major cautions to macrolide antibiotic use:
 - Hypersensitivity to clarithromycin, its excipients or other macrolide antibiotics
 - Diagnosis of long QT syndrome
 - Any event of QTc prolongation of >20ms compared to the baseline value
 - Ventricular tachycardia
 - Cardiac arrest
 - Any occurrence of severe hepatic impairment defined as AST, ALT or bilirubin >3 times ULN

Discontinuation of treatment by local clinical teams does not require withdrawal of the participant from the study and follow-up can be continued.

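### Non-fatal cardiac arrest ends clarithromycin treatment, but the protocol does not guarantee that it is counted in both arms within the 7-day safety window

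*Protocol*

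**What the plan says.** Section 9.2 identifies the hazard of most interest: "The principal risk associated in adding clarithromycin to the usual care pathway is the potential for prolongation of the QT and QTc interval", leading to arrhythmias that are mainly ventricular.

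The protocol ties cardiac arrest to that hazard in three places. Section 2.1.1 lists it, with long QT syndrome and ventricular arrhythmia, among the histories in which clarithromycin is avoided. Section 6.2 excludes people with "History of cardiac arrest". Section 7.9.1 states "Participants allocated to the intervention arm will also be withdrawn from clarithromycin treatment in the event" of certain events, and "Cardiac arrest" has its own line there, apart from ventricular tachycardia.

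On reporting, section 9.2 sets the default: "Taking the above into account, (S)AEs (except for those detailed below) will not be reported via the eCRF". There are three exceptions:

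- C. difficile infection;
- "Any incidence of sustained (>30s) ventricular arrythmias";
- a serious event that the local investigator both attributes to the trial drug and regards as unexpected.

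A note adds that an event judged related must be reported even if it occurs more than 72 hours after the drug is stopped.

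The only cardiac safety outcome in section 3.3.2 is "Ventricular arrhythmia within 7 days". The Day 7 safety items in section 7.6 refer back to the serious events defined in section 9.

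**The concern.** The protocol treats arrest as important enough to bar entry and to end treatment, but does not name it where events are reported or counted. The cardiac safety outcome depends on a ventricular rhythm having been documented. A patient who is resuscitated with no rhythm recorded, or with one recorded for 30 seconds or less, may add nothing to the comparison of the drug's stated principal risk.

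The gap also differs by arm. The remaining reporting route depends on relatedness to the trial drug, and the record of reasons for missed clarithromycin doses exists only where clarithromycin was allocated. In an open-label trial, what is recorded about an arrest could then depend on allocation. The arrhythmia result could look reassuring while non-fatal arrests were not compared. The SAP could define an analysis of arrests, but it could not recover events left only in the medical notes.

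**Working it through.** No arithmetic applies. The protocol states no expected rate of cardiac arrest or ventricular arrhythmia, and the point does not depend on power, alpha or effect size. The check is to follow each kind of event through sections 3.3.2, 6.2, 7.6, 7.9.1, 9.2 and 9.10.

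**1. Arrest with a documented ventricular arrhythmia lasting more than 30 seconds.** Reportable under the second exception in 9.2 in either arm, and counted in the safety outcome if within 7 days. No gap.

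**2. Non-fatal arrest with no such documented rhythm.**

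- *Clarithromycin arm.* Treatment stops under 7.9.1. The event is reportable under 9.2 only if judged both related and unexpected. An investigator who sees it as the known QT hazard could reasonably call it expected, which takes it off the list. Whether arrest counts as expected depends on the reference safety information, which is not shown. The event may also appear on Day 7 as a reason for missed doses.
- *Usual care arm.* No trial drug is given, so the third exception and the note on late related events cannot apply. Section 7.9.1 and the missed-dose reasons have no counterpart.
- *Both arms.* The event might enter major cardiovascular events at 90 days (3.3.2), or the Day 90 item on recurrent stroke and other vascular events (7.6). Neither is defined in the protocol, neither names arrest, and neither is a 7-day count.

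**3. Sudden death with no documented rhythm.** Section 9.10 requires every death to be recorded in the eCRF, and deaths caused by the drug to be reported as well; that sentence sets no condition of unexpectedness. The death counts in all-cause mortality and, if so classified, in cardiovascular mortality, in both arms. It is simply not shown beside the arrhythmia outcome.

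The gap is therefore in case 2: non-fatal arrest without a documented sustained ventricular rhythm, for which the protocol requires no matching record in the two arms.

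**The case against.** The strongest reply has five parts.

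- **Deaths are covered.** A reader might infer that sudden deaths go uncounted. The documents do not support that: see 9.10 and the two mortality outcomes. The IDMC also receives unblinded safety and outcome data. This part stands in full and confines the point to non-fatal arrest.
- **The list is not closed.** The third exception is open-ended, and related events after 72 hours must be reported. This is true, but both depend on relatedness to a drug that usual care does not receive.
- **Other fields may catch the event.** Section 7.6 introduces the Day 7 items as examples, the eCRF is not shown, and the Day 90 vascular items apply to both arms. Section 9.2 also has hospitalisation, or its prolongation, from the stroke or other conditions recorded at visits, so an arrest that lengthens the stay might surface there. Capture is thus possible, and to say that arrests are certainly missed would go too far. It is not required, however, and a prolonged stay does not identify an arrest. The SAP may properly define the components of major cardiovascular events; that definition is not itself at issue.
- **Stopping rules and reporting rules serve different ends.** The withdrawal list also holds QTc prolongation, severe hepatic impairment and a move to palliative care, none of which is named in the 9.2 list. This is fair: the difference between 7.9.1 and 9.2 is not by itself a contradiction. The argument for arrest rests instead on its link to the risk that 9.2 calls principal.
- **Restricted reporting is reasoned.** Section 9.2 justifies it by heavy confounding in this population, and many arrests will be due to stroke or pneumonia. This supports showing components separately, not leaving arrest unnamed.

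**Conclusion.** The point holds in a narrow form. Cardiac arrest is tied by the protocol to clarithromycin's principal risk, yet it is neither a named reportable event nor a named safety outcome. For a non-fatal arrest without a documented ventricular arrhythmia of more than 30 seconds, no two-arm capture within the 7-day window is guaranteed, and the reporting route that remains is available in one arm only.

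No size can be given. The documents contain no rate for arrest or ventricular arrhythmia. The 37% assumed for mRS 6 at 90 days in the control arm (section 10.1) says nothing about arrests in the first week. A reader might infer that uncounted events would outnumber counted ones, or that rhythm monitoring would be closer in the clarithromycin arm. The documents support neither: section 2.1.1 describes regular monitoring as part of routine care for participants generally.

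The conclusion assumes that the eCRF follows the protocol text. If it already has an arrest field completed in both arms, only the wording needs to change. This is a cheap improvement, not a flaw that threatens the primary analysis.

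**What to change.** Reconcile sections 7.9.1, 9.2 and 3.3.2 on cardiac arrest, changing reporting only:

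1. Add cardiac arrest, of any or unrecorded rhythm, to the reportable events in 9.2, irrespective of judged relatedness or expectedness.
2. Add the same item to the Day 7 eCRF for both arms, with the event date, so that events within 7 days of randomisation are counted alike.
3. Tabulate ventricular arrhythmia, cardiac arrest and sudden unexplained death within 7 days by arm, with each component shown separately beside the existing arrhythmia outcome.

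The cost is one list item, one eCRF item and one summary table, plus a few more serious-event forms. Some non-arrhythmic arrests will be included, which is why the components should stay visible. Eligibility, dosing and withdrawal rules are untouched.

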3.3.3 Exploratory outcomes

- Length of hospital stay (days) at 90 days
- Discharge destination (remains in hospital, home, care home) at 90 days
- Number of antibiotics doses received during first 7 days after randomisation
- Highest recorded CRP concentration (mg/L) during first 7 days after randomisation
- Highest recorded WBC count (x10⁹/l) during first 7 days after randomisation
- Highest recorded respiratory rate (RR)/minute during first 7 days after randomisation
- Highest recorded temperature °C during first 7 days after randomisation
- Highest recorded NEWS-2 score during first 7 days after randomisation
- Lowest recorded lowest oxygen saturations (%) during first 7 days after randomisation
- Caregiver quality of life (EQ-5D-5L)

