7.6 Follow-up assessments

The trial will comprise of 4 visits: Screening, Randomisation, Day 7 and Day 90 follow-up.

The Day 7 (+3) visit will be carried out by research staff who will collect information such as the following from case notes:

- Information on safety outcomes including *C.difficile* infection, and occurrence of defined SAEs (see section 9)
- Clarithromycin dose, doses administered and route(s) of administration (including reasons for any non-administered doses)
- Other antibiotics and doses received
- Highest CRP concentration (mg/L) to Day 7 (+3) visit
- Highest WBC count and neutrophil count (x10⁹/l) to Day 7 (+3) visit
- Highest RR (/minute) to Day 7 (+3) visit
- Highest temperature (°C) recorded to Day 7 (+3) visit
- Highest NEWS-2 score to Day 7 (+3) visit
- Lowest oxygen saturations (%) to Day 7 (+3) visit
- Oxygen requirements
- Presence of unilateral or bilateral chest signs on examination
- Findings from clinical CXR or other chest radiology
- Contact details for follow-up (participant, consented caregiver, GP)

Participants and their caregivers/GP can be contacted by telephone, email or post between 1 week and 1 month prior to the due date of the Day 90 visit to confirm contact details and ongoing participation.

The Day 90 visit will involve local data collection by the research team and a centralised assessment (+/-7 for local research staff follow-up, +/-14 for central follow-up) by video or telephone.

Local research staff will collect the following data from the medical record at Day 90 (+/-7):

- Length of hospital stay (days)
- Mortality
- Discharge destination (remains in hospital, home, care home)
- Urgent or unplanned re-admissions
- Recurrent stroke or other vascular events

The centralised assessment will then be undertaken by appropriately trained University of Manchester staff blinded to treatment allocation. This will take place via video or telephone assessment after local research staff have carried out the mortality check. They will collect information such as the following measures:

- mRS
- Quality of Life (EQ-5D-5L)
- Stroke Impact Scale (SIS)
- Home time (number of days at usual place of residence [immediately prior to their admission] at day 90)
- Health and social care resource use (index hospitalisation and post-discharge health and social care contact up to 90 days)
- Caregiver quality of life (EQ-5D-5L)
- Zarit Caregiver Burden (ZBI-12)

The Day 90 visit marks the end of the study.

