7.8 Qualitative assessments

Study drug adherence will be assessed at Day 7 (+3) and reasons for non-adherence will be documented in the eCRF.

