8.6 Dosage schedules

Participants randomised to the intervention arm will receive treatment with clarithromycin 500mg administered every 12 hours for 5 days (10 doses in total). A reduced dose of clarithromycin 250mg will be given in the event of renal impairment with eGFR <30 mL/min/1.73 m². See section 8.7 dose modification for further information. Clarithromycin treatment should commence as soon as possible after randomisation and be prescribed by an investigator (or designee) delegated this responsibility on the site delegation log in line with local requirements. It should be clear from the prescription that clarithromycin being administered as part of the CLASP study protocol.

Clarithromycin should preferably be administered via the intravenous or oral route as per the relevant SmPC. Where the enteral route is available, this should only be used if this route is considered by the

investigator to be the most appropriate route of administration. Enteral routes of administration for clarithromycin are unlicensed and may lead to variable absorption and are not generally recommended. Local guidance and requirements for administration of medicines via the enteral route as well as specific information for clarithromycin must be followed.

During the treatment period, investigators (or designees) must maintain regular oversight of clarithromycin dosing to ensure doses are administered as intended, the route of administration is appropriate and that treatment withdrawal criteria are not met. This should be evident from the participant's medical records. In the event a route of administration ceases to be available (e.g. loss of oral route due to dysphagia) or in the investigator's opinion is no longer appropriate or in-line with local policies such as IVOS, an alternate route may be considered. There is no limit to the number of times the administration route and/or presentation of clarithromycin may be changed. Changes to the presentation and route of administration must be clearly documented in the participant's usual care records.

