The clinical condition of people with stroke often fluctuates during their admission. Whilst the investigator is required to maintain regular oversight, the participant's usual care team are permitted to amend clarithromycin dose and route of administration if necessary in order to meet the changing clinical needs of the participant and ensure ongoing safety. Supervision of people receiving antibiotics is a normal part of care in stroke units. Clinical staff are not required to undertake study-specific training nor are they required to be on the site delegation log as this is within the scope of their usual practice. A Clinical Information Sheet with key information including permitted dose modifications and stopping criteria is provided for insertion into the medical notes for patients randomised to the intervention arm.

In the event a participant is discharged to home or other off-site long-term care facility such as a nursing home, any remaining oral clarithromycin doses should be provided at discharge where appropriate. In the event the oral route is not available, clarithromycin must be stopped at discharge. Clarithromycin treatment must be discontinued in the event participants are transferred to another hospital or site that is not participating in the CLASP trial.

If doses are missed and ongoing treatment is not contraindicated, study drug can be continued so a total of 10 doses are given over a maximum period of seven days.

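### Collection windows around the Day 7 (+3) visit do not match the 7-day outcomes, the permitted dosing period or the stated end of the SAE window

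*Protocol*

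**What the plan says.** **Outcomes.** Section 3.3.3 fixes the horizon of the exploratory physiological outcomes, for example "Highest recorded CRP concentration (mg/L) during first 7 days after randomisation". White cell count, respiratory rate, temperature, NEWS-2 and lowest oxygen saturation have the same 7-day horizon.

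**Collection.** Section 7.6 asks for "Highest CRP concentration (mg/L) to Day 7 (+3) visit", and words the other five measures in the same way. The row for vital signs after randomisation in Appendix 9 runs to Day 5, with a footnote referring to sections 7.5 and 7.6 for detail.

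**Dosing.** Section 8.6 specifies dosing "administered every 12 hours for 5 days (10 doses in total"). If doses are missed, treatment may continue so that "a total of 10 doses are given over a maximum period of seven days". On the start it says only this: "Clarithromycin treatment should commence as soon as possible after randomisation". Section 8.7 allows a stop and restart for low potassium or magnesium. Sections 7.6 and 7.8 and Appendix 9 place the dose and adherence record at the Day 7 (+3) visit. No Day 90 list includes a dosing item.

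**SAE window.** Sections 9.2, 9.3 and 9.4.1 end expedited reporting three days after the last trial dose, and each adds the gloss "generally, day 7 or earlier but could be up to day 10 after randomisation".

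**The concern.** One floating visit serves three purposes, and its date fits none of them exactly.

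- A maximum cannot fall, and a minimum cannot rise, as the look-back lengthens. If the cut-off is the visit date, participants are measured over different lengths of time, and some values come from outside the outcome's own definition.
- Section 10.7 plans a complier average causal effect analysis, which needs the number of doses received. The participants most exposed to an early visit are those whose courses started late and were interrupted.
- Inside the SAE window, *C. difficile* infection and sustained ventricular arrhythmia are reportable whatever their cause. After 72 hours section 9.2 asks only for events considered related. A site that took day 7 as the end would move to the narrower rule too soon.

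**Working it through.** **Inputs.** Ten doses at 12-hour intervals and a seven-day maximum (8.6); a window of 3 days, or 72 hours, after the last dose (9.2); a visit from day 7 to day 10 (7.6). The protocol fixes neither the delay to the first dose nor whether randomisation is day 0 or day 1, so both are varied below.

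**1. The plan's own figures for the window end.**
- Upper limit: 7 + 3 = day 10. This reproduces, provided the first dose is not delayed.
- Full on-schedule course: (10 − 1) × 12 = 108 h (day 4.5); 108 + 72 = 180 h = day 7.5. Counting whole days gives 5 + 3 = day 8. Day 7 or earlier does not reproduce in elapsed time.
- Nine on-schedule doses: 8 × 12 + 72 = 168 h = day 7.0. The gloss therefore fits courses stopped at nine doses or fewer.
- One missed dose made up at the end: 10 × 12 + 72 = 192 h = day 8.

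By calendar day, over the 24 possible clock hours of randomisation, a full on-schedule course gives:

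| Delay to first dose (assumed) | Window end, randomisation = day 0 | Window end, randomisation = day 1 |
|---|---|---|
| 0 h | day 7 (12 of 24), day 8 (12) | day 8 (12), day 9 (12) |
| 6 h | day 7 (6), day 8 (18) | day 8 (6), day 9 (18) |
| 12 h | day 8 (24) | day 9 (24) |
| 24 h | day 8 (12), day 9 (12) | day 9 (12), day 10 (12) |

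**2. A day-7 visit (168 h) against the window end.** It comes 180 − 168 = 12 h early for an on-schedule course, and 240 − 168 = 72 h early for a course stretched to seven days, with no start delay in either case.

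**3. A day-7 visit against the last dose.** The last dose falls at 108 h + delay + interruption. It passes 168 h only if delay plus interruption exceeds 168 − 108 = 60 h. The seven-day limit itself allows at most 60 h of interruption, so interruption alone cannot do it; some start delay is needed. With an assumed 24 h delay and 48 h interruption, the last dose is at 24 + 108 + 48 = 180 h, and the course lasts 156 h (6.5 days), within the limit. Only the doses at 168 h and 180 h could fall at or after the visit, so 8 or 9 of 10 are captured.

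**4. Peak and lowest values.** Defined horizon: 7 days. Collected horizon under 7.6: 7 to 10 days, at most 10/7 = 1.43 times the defined length. Appendix 9 vital signs: 5 days, two short of the definition. This mismatch does not depend on how days are numbered.

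**The case against.** Several stronger readings are tempting, and the protocol does not support them.

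- **That safety events are missed.** Section 9.4.1 requires listed events in the eCRF within 24 hours of awareness, whatever the visit date. Section 9.2 keeps later related events reportable, section 8.6 requires regular oversight of dosing, and Appendix 9 ticks SAEs again at local Day 90. The arrhythmia outcome runs to 7 days and the *C. difficile* outcome to 90, so neither depends on the 3-day window. This stands, although the Day 90 list in 7.6 does not itself name SAEs.
- **That the gloss is wrong for every completed course.** The operative rule, three days after cessation, is clear, and the gloss is hedged. It can hold by calendar day with randomisation as day 0 and two doses that day, and it fits courses stopped early. What remains is a poor fit for a full course in elapsed time.
- **That late doses are lost.** Section 8.10 takes adherence from hospital administration records, so later inpatient doses stay in the source. What is missing is a scheduled point for transcribing them.
- **That open-label visits bias the peak values between arms.** Nothing indicates that visit dates differ by arm, and the factor of 1.43 measures the window, not bias.

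It is also fair to say that the outcomes are exploratory and clearly defined in 3.3.3, that Appendix 9 defers to the main text, and that the complier definition may be left to the SAP.

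**Conclusion.** The point holds as a set of mismatched windows, at low severity.

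1. Followed as written, 7.6 can return a peak or lowest value over 7 to 10 days for an outcome defined over 7, and Appendix 9 gives a third window. This is the firmest part and needs no assumption.
2. A visit held on day 7 can precede the last doses and under-record compliance. This requires delay plus interruption above 60 h together with an early visit. The protocol gives no frequency; probably few participants are affected, each by one or two doses in the example.
3. The gloss on the SAE window does not fit a full on-schedule course in elapsed time (day 7.5, or day 8 by whole days). This is a wording inconsistency repeated in three sections; no loss of events is shown.

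The primary outcome and its analysis are untouched.

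**What to change.** - **7.6 and Appendix 9, physiological values:** extract peak CRP, white cell count, respiratory rate, temperature and NEWS-2, and lowest saturation, through day 7 only in both arms, whatever the date of the review. Replace the Day 5 label in Appendix 9 accordingly.
- **7.6, 7.8 and Appendix 9, review date:** do the case-note review at day 10 in both arms, which the present window already allows. Extract doses and safety events through that date, with dose dates so that the 7-day antibiotic dose count in 3.3.3 can still be derived. Add a later dose-record update for any course still running, without moving the review, so that its timing stays the same in both arms.
- **9.2, 9.3 and 9.4.1:** reconcile the parenthesis with section 8.6: about day 7.5 to 8 for a full on-schedule course, earlier if stopped early, and up to day 10 if extended, plus any delay to the first dose. State whether randomisation is day 0 or day 1.

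No dose or treatment rule changes. The cost is protocol and eCRF wording and data entry up to three days later. Day 10 is the last day of the current window, so sites lose scheduling slack unless a short tolerance follows it; fixed cut-off dates would keep the extracted data the same.
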